2.1 Study Objectives

2.1.1 Primary Objective

The primary aim of the study is to estimate the objective response rate (ORR).

2.1.2 Secondary Objectives

The secondary objectives of the study will be analyzed separately and are:

- Clinical benefit rate (CBR)
- Duration of Response (DOR)
- Toxicity profile

In addition, exploratory studies will be performed on available data, with the aim:

- Discovering markers that predict treatment benefit

2.2 Study Design

2.2.1 Stage I futility analysis

If at least one patient in the first stage has an objective response, the study will proceed to Stage II (*expansion cohort*), otherwise the study will stop for futility.

2.2.2 Stage II

If ≥ 3 patients of the combined stage I and II evaluable patients have an objective response, the study therapy will be considered for further testing.

2.3 Sample Size Justification

The hypothesis tested to determine the activity of Dual Immune Checkpoint Blockade with Durvalumab plus Tremelimumab expressed in terms of ORR:

H₀: ORR < 0.05

H_A: ORR > 0.20

With the specified null and alternative hypotheses, a type I error rate of 0.10 one-sided and power of 0.80 to reject H₀ if the true response rate is 20%, a Simon two stage design consists of initially treating 12 evaluable patients. Enrolment should end for an inadequate response (futility) if no patients have an objective response. If at least one patient has an objective response, enrolment continues to a total of 21 patients. If at least 3 responses are seen (ORR > 0.143), the treatment will be considered worth testing further.

3. General Analysis Definitions

Data will be analyzed using SAS v 9.4.

Descriptive statistics will be tabulated as follows:

- Categorical data will be summarized in contingency tables presenting frequencies and percentages.
- Continuous data will be summarized using number of non-missing values (n), mean, standard deviation, median, minimum and maximum values.

3.1 Study Period and Visit Window Definitions

3.1.1 Study Periods

The accrual period is expected to be 24 months.

Enrolled patients will receive the combination of tremelimumab (75 mg IV infusion) and durvalumab (1500 mg IV infusion) on Day 1 for 4 cycles. Beginning with Cycle 5 through Cycle 12, patients will receive durvalumab alone (1500 mg/IV infusion) on Day 1 of each 28 day cycle.

All AEs will be recorded from the first dose of study therapy until 90 days after the last dose of study therapy or at the cessation of study therapy if the patient initiates new anti-cancer therapy, whichever is earlier.

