Blood samples ^h	X (Day 15/Cycle 1 and Day 1/Cycles 2, 4)	X (Day 1, Cycle 6)	
Tumor sample ⁱ	X (Following completion of Cycle 2) [at 8 weeks]		

Table 2 continued on next page.

Table 2. Tests, exams, and other requirements **following study entry** (continued)

- a** At the discretion of the investigator, additional exams, bloodwork, x-rays, ECGs, scans, and other testing may be performed as clinically indicated.
- b** *Note:* Confirmation must be made that resolution of all hematologic, gastrointestinal and genitourinary toxicities are < Grade 2 before beginning the first study therapy infusion. Updated H&P with exams, adverse event assessment, and assessments during therapy and follow-up by physician or other appropriate healthcare professional (on FDA Form 1572).
- c** Vital signs (temperature, blood pressure, pulse rate, and respiratory rate) will be measured and recorded. On study therapy treatment days, vital signs will be measured within an hour prior to start of tremelimumab and durvalumab administration, at 30 minutes during the infusion (\pm 5 minutes), at the end of infusion (+ 5 minutes), and at 30 minutes (\pm 5 minutes) and 60 minutes (\pm 5 minutes) post-infusion. If the infusion takes longer than 60 minutes, then blood pressure and pulse measurements should follow the time increments as outlined at the end of the infusion or more frequently if clinically indicated. For subsequent doses of study therapy, there will be a 30 minute observation period and vital sign check between tremelimumab and durvalumab doses to monitor potential infusion-related reactions. See [Table 4](#).
- d** AE assessments 90 days (+/- 14 days) after the last dose of study therapy. Should the patient stop study therapy (e.g. due to disease progression or second primary) and begin a new treatment *prior* to the last dose of durvalumab assessment, AE assessments should be collected *only* up to the date the new therapy begins. See [Section 10.7](#).
- e** The same imaging method (PET/CT scan, CT scan or MRI), used at baseline should be used every 2 cycles from start of therapy. Assessment of measurable disease is every 2 cycles by RECIST 1.1. See [Section 11.0](#).
- f** CEA levels should be obtained every 2 cycles to correlate with disease imaging.
- g** If TSH abnormal, (outside normal range) obtain free triiodothyronine (T₃) and thyroxine (T₄).

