Radiation-induced liver disease (RILD) is a clinical syndrome of anicteric ascites, hepatomegaly and elevation of alkaline phosphatase relative to other transaminases that may occur 2 weeks to 3 months following radiation to the liver ([Guha 2011](#)). An increase in ALP must be at least 2-fold above the baseline alkaline phosphatase. RILD is unlikely to occur after a mean liver dose of approximately 30 Gy in conventional fractionation. By maintaining a low mean liver dose and sparing a “critical volume” of liver from radiation, stereotactic delivery techniques allow for the safe administration of higher tumor doses. Patients with pre-existing liver disease (e.g., Child-Pugh score of B or C) are at an increased risk ([Guha 2011](#)). Treatment of RILD with repeat paracenteses, diuretics, and close follow-up is recommended ([Guha 2011](#)). See [Table 7](#) for specific study therapy dose modification instructions.

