10.7 Expedited reporting instructions

10.7.1 *Time period for reporting SAEs and other events requiring expedited reporting*

- All SAEs and other events as noted in [Sections 10.3](#) and [10.4](#) regardless of relationship to study therapy will be reported in an expedited manner as described in [Section 10.7](#). Reporting SAEs (and other applicable events) regardless of relationship to study therapy begins with the first dose of study therapy and continues until 90 days after the last dose of study therapy.
- Any SAE assessed as related to study participation (e.g., protocol-mandated procedures) will be recorded from the time a patient consents to participate in the study up to and including any follow-up contact.
- Following the AE assessment 90 days after the last dose of study therapy, only SAEs determined to be related to study therapy will be reported in an expedited manner using FC-9 Form SAER.
- The investigator must follow up on all SAEs until the events have subsided, until values have returned to baseline, or until the condition has stabilized.

10.7.2 *Reporting instructions*

- All SAEs and other events requiring expedited reporting (e.g., AESIs \geq Grade 2) must be reported using FC-9 Form SAER (eCRF) and submitted to DSSM within 24 hours of the study site personnel's initial notification of the event.
- When reporting potential Hy's Law cases, Form SAER should include the following:
 - Seriousness Criteria = Important Medical Event
 - Assessments and narrative: Include the term “Potential Hy’s Law case” in the narrative; the text should also detail what additional study results are available at the time of reporting and what other studies are planned or results pending to further investigate alternative causes of the abnormal ALT/AST or bilirubin that triggered the report. The timing of planned patient follow-up should also be noted.
- NSABP will forward expedited report forms that meet reporting requirements to the FDA and to Astra Zeneca/MedImmune Pharmacovigilance.
- Investigators are responsible for reporting AEs that meet specific criteria to their local IRBs.

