10.8 Time period and frequency for routine reporting of AEs

- Patients will be monitored for the occurrence of AEs at each scheduled assessment and during any contact with the patient during the study.
- All AEs, including SAEs and other AEs that have been reported on FC-9 Form SAER, regardless of relationship to study therapy, will be recorded on Form AE of the CRF from the first dose of study therapy until 90 days after the last dose of study therapy.

- If the patient stops study therapy and begins a new treatment, AE assessments should be collected *only* up to the date the new therapy begins.
- For routine reporting, **all \geq Grade 1 AEs** will be reported on Form AE of the CRF.
- The investigator must follow up on all AEs until the events have subsided, until values have returned to baseline, or until the condition has stabilized.
- Following the AE assessment 90 days after the last dose of study therapy, routine reporting is no longer required. (See [Section 10.4](#) for expedited reporting requirements.)

10.9 **Documentation requested following death**

For deaths that occur within 30 days of the last dose of study therapy:

- Autopsy reports should be secured whenever possible and should be submitted to DSSM.
- A copy of the death certificate should be forwarded to DSSM if it is readily available or if it contains important cause-of-death information that is not documented elsewhere.
- Submit the last clinic/office note made before the death or the investigator's note summarizing events resulting in death.

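### For patients who start new anti-cancer therapy, SAP 3.1.1 closes the adverse-event window at an undefined cessation of study therapy, earlier than protocol 10.8 and Table 2 footnote d

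*Combined protocol and SAP*

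**What the plan says.** Four places bear on when AE capture ends.

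- **SAP 3.1.1** records AEs from first dose to 90 days after the last dose, "or at the cessation of study therapy if the patient initiates new anti-cancer therapy, whichever is earlier". Cessation is not defined; it could be the last infusion or the decision to stop.
- **Protocol 10.8** (routine reporting) has two bullets. One says that all AEs, including serious AEs (SAEs) and other events already on Form SAER, "will be recorded on Form AE of the CRF from the first dose of study therapy until 90 days after the last dose of study" treatment. The next says that, once a patient has stopped and moved to a new treatment, "AE assessments should be collected *only* up to the date the new therapy begins".
- **Table 2 footnote d** (protocol 5.0) calls for "AE assessments 90 days (+/- 14 days) after the last dose of study therapy", repeats the cut at the start of new therapy, and refers the reader to Section 10.7.
- **Protocol 10.7.1** (expedited reporting) says that reporting of SAEs and other applicable events, whatever their cause, "begins with the first dose of study therapy and continues until 90 days after the last dose of study therapy". It contains no new-therapy cut-off. After that, only SAEs related to study therapy are reported, with no end date. Section 10.4.2 puts AESIs of Grade 2 or higher on the same route.

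On the analysis side, SAP 6.2 defines a treatment-emergent AE by its start only (on or after first dose). SAP 3.5 states that nothing has changed from the protocol's planned analyses.

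**The concern.** A rule that stops counting AEs when new treatment starts is an ordinary way to protect attribution, and that is the protocol's rule. The SAP's rule differs. It closes the window before the new treatment, during time when study therapy is the only trial or subsequent treatment the patient has received. It also makes the window depend on a later event. Take two patients with the same AE on the same day after the last dose: if one later starts new therapy and the other does not, SAP 3.1.1 counts the event for the second only.

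Safety is a secondary aim (protocol 3.2.3), and the protocol itself expects some delayed toxicity. Section 8.6.1 describes radiation pneumonitis arising weeks to months after treatment, and 8.6.2 describes a liver syndrome "that may occur 2 weeks to 3 months following radiation to the liver". All patients have already progressed on chemotherapy, so a further treatment after this one is foreseeable, though the documents give no figure for how often or how soon.

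At stake is whether the AE tables (SAP Appendix 1, Tables 04.01 to 04.07) reflect what sites collected, and whether SAE counts agree between expedited reports and tables.

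**Working it through.** The plan states no figure on this point, so the check compares the rules directly.

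**Inputs.** Let g be the days from last dose to start of new therapy, and c the days from last dose to cessation as the SAP intends it, with 0 ≤ c ≤ g. Neither is given in the documents. The 90-day limit is common to all the rules.

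**Length of capture after the last dose, for a patient who starts new therapy:**

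- SAP 3.1.1: min(c, 90)
- Protocol 10.8 and footnote d: min(g, 90)
- Protocol 10.7.1, SAEs and other expedited events: 90

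The SAP-versus-protocol gap for routine AEs is therefore min(g, 90) − min(c, 90). The stretch in which SAEs are reportable under 10.7.1 but fall after the 10.8 new-therapy cut-off is 90 − min(g, 90). For a patient who starts no new therapy, every rule gives 90 days and there is no discrepancy.

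**Range over assumed g, reading cessation as the last dose (c = 0):**

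| g (days, assumed) | SAP 3.1.1 | Protocol 10.8 | Gap | SAE days beyond the 10.8 cut-off |
|---|---|---|---|---|
| 14 | 0 | 14 | 14 | 76 |
| 28 | 0 | 28 | 28 | 62 |
| 42 | 0 | 42 | 42 | 48 |
| 60 | 0 | 60 | 60 | 30 |
| 90 | 0 | 90 | 90 | 0 |

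**Worked example (assumed patient).** Cycles are 28 days, so Cycle 2 Day 1 is day 29, four weeks after first dose. Suppose that is the last dose, the scan after Cycle 2 at week 8 shows progression, study therapy stops then, and new therapy begins at week 10.

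- Protocol 10.8 closes at week 10, so g = 6 weeks = 42 days.
- SAP 3.1.1 closes at week 4 if cessation is the last dose: gap 10 − 4 = 6 weeks.
- SAP 3.1.1 closes at week 8 if cessation is the decision to stop: gap 10 − 8 = 2 weeks.
- Protocol 10.7.1 closes at day 29 + 90 = day 119, about week 17.

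**Which source feeds the tables.** Consider an SAE, or an AESI of Grade 2 or higher, between week 10 and week 17. It is reportable on Form SAER under 10.7.1. The first of the two 10.8 bullets puts it on Form AE as well; the second stops AE assessments at week 10. SAP 6.2 would count it, since it sets no end date; SAP 3.1.1 would not. The SAP does not say which form or window supplies its AE and SAE outputs, so two programmers could produce different counts in good faith.

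**The case against.** The strongest reply is that SAP 3.1.1 is descriptive. It sits under a study-periods heading beside the dosing schedule and says what will be recorded, not what will be dropped. Sites record under the protocol, SAP 3.1.2 defers follow-up requirements to protocol section 5 (which holds footnote d), SAP 6.2 sets no end date, and listings of all AEs are promised. This stands to a large extent. A reader might infer that late toxicity is lost or will be understated, and the documents do not support that: the protocol collects the events, and exclusion follows only if 3.1.1 is used as a filter. But nothing in the SAP says that it is not a filter, and 3.1.1 and 6.2 point different ways.

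Second, expedited and routine reporting serve different purposes, so a longer SAE window is not in itself an error. That stands. What remains is the conflict between the two bullets of 10.8, and a footnote d that refers to 10.7 for a cut-off which 10.7.1 does not contain.

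Third, delayed immune toxicity is comparatively well protected: AESIs of Grade 2 or higher follow the SAE route to 90 days, and related SAEs are reported beyond that. This stands, and it narrows the exposed events to non-serious AEs that are not Grade 2 or higher AESIs.

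Fourth, a reader might set the liver-syndrome window (week 2 to about week 13, or 11 weeks) against a SAP cut at week 4 and conclude that 9 of the 11 weeks are missed. That overstates it. It takes cessation as the last dose, and it counts weeks 10 to 13, which routine collection under 10.8 also excludes. It applies to liver irradiation, while the irradiated lesion may be in the lung (Appendix B 1.3). The part due to the SAP alone is 6 weeks at most in the example, or 2 on the other reading.

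Finally, the SAP is a draft that cites the November 7, 2016 protocol and still ends durvalumab at Cycle 12, where the protocol now runs to Cycle 24. The sentence may simply be outdated; the 2016 wording is not available to check. That may explain the mismatch but does not remove it.

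**Conclusion.** The inconsistency is real and should be corrected before the safety tables are programmed. It affects only patients who start new anti-cancer therapy. For them SAP 3.1.1 closes the AE window earlier than the protocol does, at an undefined point, and SAP 3.5 does not declare the difference. The consequence is exclusion from, or inconsistent counting in, the tables, not loss of data.

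The size depends on c and g, which the documents do not give. In the example the gap is 2 to 6 weeks, assuming no dosing beyond the first progression scan (protocol 11.0 allows it in some patients) and new therapy two weeks after that scan. The upper limit is 90 days, reached only if cessation means the last dose and new therapy starts 90 days or more later. The number of patients affected cannot be estimated.

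The AE window does not enter the two-stage response-rate design, so the sample size, stopping rule and final decision rule are unaffected.

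**What to change.** 1. In SAP 3.1.1, end AE capture at the earlier of two dates: 90 days after the last dose, or the start of new anti-cancer therapy. This removes the undefined term.
2. State the same end of window in SAP 6.2.
3. Reconcile protocol 10.8 and Table 2 footnote d with 10.7.1, so that both say how SAEs and AESIs of Grade 2 or higher are recorded between the start of new therapy and day 90.
4. In the SAP, tabulate those events consistently to 90 days, flag those that begin after new therapy, and name the form (AE or SAER) that supplies each table and listing.

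The cost is wording. Routine events are already collected to the start of new therapy and expedited events to 90 days. The flag needs the start date of new therapy, which the cut-off in 10.8 already requires sites to know; the documents do not show whether it is an eCRF field, so that should be confirmed.

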3.1.2 Entry, Treatment, and Follow-up

Requirements for study entry and during treatment and follow-up are outlined in section 5 of the protocol.

3.2 Planned Analyses

3.2.1 Stage I Analysis

The first analysis of ORR will be performed when 1 or more stage I patients have an objective response or 2 years after the last stage I patient is entered, whichever comes first.

3.2.2 Final Analysis

The second and final analysis of ORR will be performed when all patients have completed protocol therapy.

3.3 Definition of Analysis Populations

3.3.1 Intent-to-Treat Population (ITT)

The Intent-To-Treat population (ITT) will consist of patients who complete both Cycle 1 and Cycle 2, and undergo the first restaging scan after Cycle 2 for the determination of tumor response will be determined as evaluable. Non-evaluable patients will be replaced.

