1.0 OVERVIEW OF STUDY DESIGN

The FC-9 study is designed as a phase II, open label, single arm study of the dual immune checkpoint blockade with the combination of durvalumab and tremelimumab following hypofractionated palliative radiation in patients with microsatellite stable (MSS) metastatic colorectal cancer (mCRC) who have progressed on chemotherapy. The primary aim is to determine the anti-tumor efficacy of the dual immune checkpoint blockade with durvalumab plus tremelimumab. The secondary aims are to determine the clinical benefit rate, duration of response, tolerability and correlates of response. Tumor response at unirradiated target lesions will be measured at baseline and every 2 cycles using RECIST 1.1.

[figure not shown]
Following three doses of hypofractionated palliative radiation (Days -2, -1, and Day 0 prior to Cycle 1), patients will receive the combination of tremelimumab (75 mg IV infusion) and durvalumab (1500 mg IV infusion) on Day 1 for 4 cycles. Beginning with Cycle 5 through Cycle 24, patients will receive durvalumab alone (1500 mg/IV infusion) on Day 1 of each 28 day cycle.

Toxicity will be graded according to the National Cancer Institute (NCI) Common Terminology Criteria for Adverse Events version 4.0.

The sample size will be between 12 and 21 evaluable patients. Patients who complete both Cycle 1 and Cycle 2, and undergo the first restaging scan after Cycle 2 for the determination of tumor response will be determined evaluable. Non-evaluable patients will be replaced. Twelve evaluable patients will be treated in the first stage of the study. If there are no responses among the 12 evaluable patients, the study will be terminated. If the study goes on to the second stage, a total of 21 evaluable patients will be studied. If the total number responding is less than or equal to 2, the combination will be rejected. If 3 or more responses are observed after the second stage of the study, the combination will be considered for further study.

Submission of tumor tissue and blood samples for FC-9 correlative science studies will be a study requirement for all patients. Requirements will include archived tumor samples from the diagnostic biopsy; additional biopsies of fresh tissue from an accessible lesion prior to radiation therapy and after 2 cycles of study therapy; and blood sample collections.

Figure 1
FC-9 Schema

‡Hypo-fractionated stereotactic body radiation therapy (SBRT)

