14.2 Statistical design and sample size analysis

The optimal two-stage design ([Simon 1989](#)) to test the null hypothesis that $ORR_0 \leq 0.05$ versus the alternative that $ORR_A \geq 0.20$ has an expected sample size of 16.14 and a probability of early termination of 0.54. If the combination study therapy is actually not effective, there is a 0.080 probability of concluding that it is (the target for this value was $\alpha = 0.10$). If the combination study therapy is actually effective, there is a 0.197 probability of concluding that it is not (the target for this value was $\beta = 0.20$).

Patients who complete both Cycle 1 and Cycle 2, and undergo the first restaging scan after Cycle 2 for the determination of tumor response will be determined as evaluable. Non-evaluable patients will be replaced.

After testing the study therapy combination on 12 evaluable patients in the first stage, the trial will be terminated if 0 patients respond. If the trial goes on to the second stage, a total of 21 evaluable patients will be studied. If the total number responding is less than or equal to 2, the combination is rejected. If 3 or more responses are observed ($ORR \geq 14.3\%$) after the second stage of the study, the combination will be considered for further study.

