3.5 Changes to Protocol

No change has been done from the analyses planned in the protocol.

4. Study Patients

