7.1 Primary Analysis of Stage II: Objective Response Rate

The ITT population will be used to test the effects of therapy on ORR. The best overall response is the best response recorded from the start of the treatment until disease progression/recurrence (taking as reference for progressive disease the smallest measurements recorded since the treatment started). Confirmation of complete or partial response IS NOT required.

A summary table presenting % of patients with a best overall response of CR, PR, SD and PD will be made. ORR will be calculated as % of patients with CR or PR at any time during the treatment (including unscheduled assessments). The 95 % confidence interval of the ORR proportion will be reported using exact method based on the binomial distribution (Clopper-Pearson method). The denominator will be the number of patients in the ITT population.

The primary objective of the trial will be reached if at least 3 responses are observed among 21 evaluable patients (14.3%).

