7.2.1 Clinical Benefit Rate

CBR is defined as the proportion of patients with no progression or death at 16 weeks.

The 95% confidence interval of the CBR will be reported using exact method based on the binomial distribution (Clopper-Pearson method). The denominator will be the number of patients in the ITT population.

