Appendix 1: List of Statistical Tables

Appendix 2: List of Data Listings

Appendix 1: List of Statistical Tables

Table Number	Table Title	Population
Table 01.01	Patient Disposition	All enrolled patients
Table 01.02	Completion Status and Discontinuation from study drugs	ITT
Table 01.03	Completion Status and Discontinuation from the Study	ITT
Table 02.01	Demographic and Other Baseline Characteristics	ITT
Table 03.01	Extent of Exposure	ITT
Table 04.01	Summary of Adverse Events	Safety
Table 04.02	Grade 1/2 Adverse Events by SOC and PT	Safety
Table 04.03	Grade 3/4 Treatment-Emergent Adverse Events by SOC, PT	Safety
Table 04.04	Adverse Events Leading to Discontinuation of Study Therapies, by SOC and PT	Safety
Table 04.05	Fatal Adverse Events by SOC and PT	Safety
Table 04.06	AEs leading to Death by SOC and PT	Safety
Table 04.07	Deaths	Safety
Table 05.01	Best overall response	ITT
Table 05.02	Objective Response Rate	ITT
Table 05.03	Clinical Benefit Rate at 16 weeks	ITT
Table 05.04	Duration of Response	ITT
Figure 05.05	Kaplan-Meier Duration of Response Plot	ITT

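### The SAP's 'ITT' set is the protocol's response-evaluable set; ORR and CBR are planned on it alone, with no all-treated rate

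*Combined protocol and SAP*

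**What the plan says.** Protocol 1.0 sets the evaluability condition: patients must complete Cycles 1 and 2 and "undergo the first restaging scan after Cycle 2 for the determination of tumor response will be determined evaluable". Protocol 14.2 repeats it and adds "Non-evaluable patients will be replaced". Neither section calls this set intent-to-treat.

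SAP 3.3.1 gives the same set a new name: "The Intent-To-Treat population (ITT) will consist of patients who complete both Cycle 1 and Cycle 2, and undergo the first restaging scan". SAP 3.5 then records "No change has been done from the analyses planned in the protocol".

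The set is used as follows.

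- **ORR (SAP 7.1):** "The denominator will be the number of patients in the ITT population".
- **CBR (SAP 7.2.1):** "CBR is defined as the proportion of patients with no progression or death at 16 weeks", with the same denominator.
- **Efficacy tables (SAP Appendix 1):** Tables 05.01 to 05.04 (best response, ORR, CBR, duration of response) are all on ITT.
- **Other tables on ITT:** 01.02 ("Completion Status and Discontinuation from study drugs"), 01.03 (completion of the study) and 03.01 (exposure).

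SAP 3.3.2 defines a Safety population of everyone who received at least one dose. Appendix 1 uses it only for the adverse event and death tables. The text of SAP section 6 puts safety on the ITT population, in square brackets, which disagrees with Appendix 1.

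**The concern.** Membership of this set depends on what happens after treatment starts: about eight weeks of therapy completed and a scan obtained. The routes out of it are death, symptomatic deterioration (protocol 11.3), early progression, toxicity, withdrawal of consent and loss to follow-up (protocol 8.2.2). Several of these are themselves treatment failures.

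The label tells the reader the opposite. A rate headed ITT will normally be taken to cover everyone treated. The primary aim in protocol 3.1 likewise concerns patients with MSS metastatic disease who progressed on chemotherapy, with no condition that they complete two cycles.

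For CBR the exclusion works against the endpoint's own definition. A death in week 12, after the Cycle 2 scan, is a failure. A death in week 5 removes the patient from the denominator.

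At stake is the headline response rate and its interval as an estimate for treated patients. The go/no-go decision is not affected.

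**Working it through.** **Step 1: do the plan's own figures hold?**

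Inputs from protocol 14.2: 12 evaluable patients in stage 1, stop at 0 responses; 21 in total, success at 3 or more; null ORR 0.05, alternative 0.20.

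Let X1 be the responses among the first 12 and X2 those among the next 9.

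P(success) = P(X1=1)·P(X2≥2) + P(X1=2)·P(X2≥1) + P(X1≥3)

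- At 0.05: 0.3413 × 0.0712 + 0.0988 × 0.3698 + 0.0196 = 0.0243 + 0.0365 + 0.0196 = 0.0804 (stated 0.080).
- At 0.20: 0.2062 × 0.5638 + 0.2835 × 0.8658 + 0.4417 = 0.8033, so the type II error is 0.1967 (stated 0.197).
- Early termination at 0.05: 0.95^12 = 0.5404 (stated 0.54).
- Expected sample size: 12 + 9 × (1 − 0.5404) = 16.14 (stated 16.14).

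All four reproduce. They apply to evaluable patients, which is how the rule is worded.

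**Step 2: who is in each rate?**

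| Event in a treated patient | In the 'ITT' rates? |
|---|---|
| Progression shown at the scan, both cycles completed | Yes, as non-responder and CBR failure |
| Death between that scan and week 16 | Yes, as CBR failure |
| Death before completing Cycle 2 and the scan | No |
| Deterioration, toxicity stop, withdrawal or loss before that point | No |

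**Step 3: how far can the rates move?**

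The documents give no non-evaluable rate, so the number replaced, k, is an assumption. If no replaced patient responds, the all-treated rate is the evaluable rate × 21/(21+k). For k = 3 the factor is 21/24 = 0.875, a relative fall of 12.5%. For k = 6 it is 21/27 = 0.778, a fall of 22.2%. Intervals are Clopper-Pearson 95%.

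| Replaced | ORR at minimum success | CBR, illustrative 6 successes |
|---|---|---|
| 0 | 3/21 = 14.3% (3.0 to 36.3) | 6/21 = 28.6% (11.3 to 52.2) |
| 3 | 3/24 = 12.5% (2.7 to 32.4) | 6/24 = 25.0% (9.8 to 46.7) |
| 6 | 3/27 = 11.1% (2.4 to 29.2) | 6/27 = 22.2% (8.6 to 42.3) |

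The direction is not guaranteed. SAP 7.1 counts unscheduled assessments, so a replaced patient can have a documented response. If one of three does, the all-treated ORR is 4/24 = 16.7% (4.7 to 37.4), above 14.3%.

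**Step 4: sensitivity of the decision rule.**

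This is not a type I error defect, because the documents do not set a null on all treated patients. Suppose the all-treated ORR were 5% and a share k/(21+k) of treated patients were non-evaluable. With e = 21/(21+k) and replaced patients responding at rate q, the evaluable rate is (0.05 − q(1 − e))/e. Putting that rate through the formula in step 1 gives the chance of declaring success:

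| q | Results |
|---|---|
| 0 | 0.080, 0.099, 0.109, 0.142 for k = 0, 2, 3, 6 |
| 2.5% | 0.094, 0.099, 0.104 for k = 3, 4, 5 |
| 5% | 0.080 for every k |

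**The case against.** The protocol itself chose evaluable patients and replacement, and the decision rule follows it; SAP 2.2.2 requires that at least three "patients of the combined stage I and II evaluable patients have an objective response". On that reading SAP 3.5 is right in substance for ORR, since only the name changed. SAP 3.3.1 uses the word evaluable within the definition, and SAP 7.1 speaks of 21 evaluable patients, so the restriction is disclosed. Table 01.01 gives the numbers treated and evaluable. Tables 04.04 to 04.07 cover adverse event discontinuations and deaths on the Safety population. The appendix of data listings covers all patients for response indicators, completion and drug administration, so in a trial this small a reader could count an all-treated rate by hand. The SAP is marked as a draft, the shifts are small beside intervals some 30 points wide, and their size is hypothetical.

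Much of this stands. The decision rule needs no change, the data will be captured, and step 4 shows a sensitivity, not an error. But a listing gives no rate and no interval. Nor does disclosure inside a definition correct a label that heads every efficacy table. Non-AE reasons for early discontinuation, and exposure in patients who stopped in Cycles 1 and 2, would appear only in listings.

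A separate difference also needs settling. Protocol 3.2.1 counts any PR or CR plus stable disease at 16 weeks, whereas SAP 7.2.1 requires freedom from progression and death at 16 weeks. That does not bear on which patients belong in the denominator.

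**Conclusion.** The concern holds and should be fixed. The SAP gives the name ITT to a set selected on post-baseline events, computes ORR and CBR on nothing else, and drops early deaths from a CBR that is meant to count them as failures. The rates overstate benefit for treated patients if those excluded are mostly non-responders. At the success boundary that means 1.8 percentage points with three replaced (14.3% to 12.5%) and 3.2 points with six (14.3% to 11.1%). The number replaced and the absence of responses among them are assumptions, and the 4/24 case shows the sign can reverse. The intervals overlap widely, so the effect is on the point estimate and its interpretation. The two-stage design, its alpha of 0.080 and the 12/21 rule are correct for the evaluable set they are stated on.

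**What to change.** 1. Rename the SAP 3.3.1 set 'response-evaluable'. Keep the decision rule and Tables 05.01 to 05.04 on it, marked as the basis of the decision.
2. Add two supportive tables, all-treated ORR and all-treated CBR, with Clopper-Pearson 95% intervals on the SAP 3.3.2 Safety population. That set suits the purpose because protocol 8.1 treats patients who cannot receive Dose 1 as screen failures.
3. In those tables, count as a failure every treated patient without a documented response (ORR) or without documented progression-free status at 16 weeks (CBR), whatever the reason. A documented response in a replaced patient counts as a response. Use the SAP 7.2.1 definition of CBR, and settle its difference from protocol 3.2.1 before programming.
4. Put Tables 01.02, 01.03 and 03.01 on all treated patients.
5. Change the SAP section 6 text to the Safety population, to agree with Appendix 1.

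The cost is SAP wording, two new tables and a changed population for three existing ones. Design, sample size, replacement rule and decision rule stay as they are. The drawback is that two rates per endpoint must be reported, and the all-treated one will usually be the lower.
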